Objective(s):	
The primary objective of this open-label study is to continue to provide aripiprazole intramuscular (IM) Depot treatment (400 mg or 300 mg) to subjects with schizophrenia completing the 52-week, open-label safety and tolerability Study 31-08-248 (hereafter referred to as Study 248). Subjects can receive this treatment until aripiprazole IM Depot is commercially available in any dosage (including generic formulation[s]) in the country that the study is being conducted or until the study end date of 31 Dec 2018 is reached.
 
The secondary objective is to collect long-term safety data on aripiprazole IM Depot in addition to what was collected in Study 248 (52-weeks).
	
Trial Design:	
This is an open-label, multicenter rollover non-comparative trial designed to continue to provide aripiprazole IM Depot (400 mg or 300 mg) to adult subjects with schizophrenia who completed aripiprazole IM Depot treatment in Study 248. The decision to enroll into the long-term open-label study will be a joint decision by the investigator and subject. No subjects who discontinued or did not complete Study 248 are allowed to enroll in Study 31-10-270 (hereafter referred to as Study 270).
 
Eligible subjects will enter this study directly after completing the End of Treatment visit (Week 52) of Study 248. The End of Treatment evaluations conducted at the last study visit for Study 248 will serve as the baseline evaluations for Study 270.
 
Subjects in this study will continue to receive aripiprazole IM Depot every month (study months are every 4 weeks which is defined as 28 [-2/+10] days) as a continuation of their previous monthly dose in Study 248. The minimum interval of 26 days and maximum interval of 38 days between injections is to ensure that therapeutic plasma concentrations of aripiprazole are maintained. The monthly dose can be modified, either reduced from 400 mg to 300 mg to address tolerability or increased from 300 mg to 400 mg to address efficacy, at the discretion of the investigator.
 
Following the baseline visit, subjects will receive monthly injections and at the same visit, adverse events (AEs) and concomitant medications will be recorded and the Columbia Suicide Severity Rating Scale (C-SSRS) will be completed.
 
Every 3 months, all of the monthly assessments will be completed along with a urine pregnancy test for women of childbearing potential (WOCBP). Every 6 months, all of the 3-month assessments will be completed along with the Clinical Global Impression - Severity (CGI-S) scale, vital signs, and extrapyramidal symptoms (EPS) assessments (including the Abnormal
	

Protocol 31-10-270

Involuntary Movement Scale [AIMS], Simpson-Angus Scale [SAS], and Barnes Akathisia Rating Scale [BARS]). At the 12-month visit, all of the 6-month assessments will be completed along with clinical laboratory tests and assessments of body weight, height, and waist circumference.

Urine drug screening and blood alcohol testing will be obtained at baseline and can be re-obtained at the investigator's discretion at any time during the study. A Visual Analog Scale (VAS) for subject-reported rating of pain at the most recent injection site and the investigator's assessment for pain, redness, induration, and swelling of the most recent injection site will be performed at baseline and may be reassessed at the discretion of the investigator. Clinical laboratory tests, physical examination, and electrocardiogram (ECG) obtained at baseline may also be performed at the discretion of the investigator based on clinical necessity.

A Study Completion visit or Early Termination visit (-2/+10 days) will include the following assessments: C-SSRS, AEs, concomitant medications, a urine pregnancy test for WOCBP, CGI-S, vital signs, EPS assessments (AIMS, BARS, SAS), clinical laboratory tests, and body height and weight.

A 30-Day Post Treatment Follow-up phone call will be made 30 days (± 3 days) after it has been determined that the subject will no longer participate in this study and will include questions about any AEs that have occurred and any concomitant medications taken since the last visit.

No oral antipsychotic rescue medication (including aripiprazole) is allowed in this study. If a subject experiences an exacerbation of psychotic symptoms, the investigator should assess the suitability of the subject's continuation in the study and ensure that the subject is treated appropriately. If the investigator deems that other antipsychotic therapy is warranted, the subject should be discontinued from this study.

Aripiprazole IM Depot treatment in this open-label rollover study will continue until there are clinical and/or administrative reasons for discontinuation of the subject's study treatment or until the study end date of 31 Dec 2018 is reached, whichever occurs first.

Clinical reasons for discontinuing study treatment include, but are not limited to: the subject voluntarily withdrawing consent; the subject becoming lost to follow-up; if a subject misses 2 consecutive injections at any time in the study or if a subject misses 3 injections in a 52-week time period; or the investigator determines that the subject is no longer receiving benefit from aripiprazole IM Depot. Administrative reasons for discontinuing study treatment include, but are not limited to: aripiprazole IM Depot becomes commercially available in any dosage (including a generic formulation) in the country where the study is being conducted, the commercial availability of aripiprazole IM Depot is terminated by the sponsor, or until the study end date of 31 Dec 2018 is reached, whichever occurs first.

Once aripiprazole IM Depot becomes commercially available in any dosage (including generic formulation[s]) in the country where the subject is participating in the study or the commercial availability of aripiprazole IM Depot is terminated by the sponsor, study treatment will be discontinued within approximately 6 weeks of the subject's previous injection for clinical transition purposes.

If the sponsor terminates the study prior to 31 Dec 2018 for any reason other than commercial availability, investigators in some countries where the sponsor has limited or delayed commercialization plans, or where no

Protocol 31-10-270

	commercialization activity is anticipated, may be eligible to participate in a managed access program until aripiprazole IM Depot is commercially available in their country or until 31 Dec 2018.
Subject Population:	
The subject population will be comprised of subjects who have completed Study 248 and in the investigator's judgment may benefit from continued participation in an aripiprazole IM Depot study, in countries where aripiprazole IM Depot is not commercially available.
 
It is anticipated that approximately 500 to 800 subjects from Study 248 will enroll in this study.

Inclusion/Exclusion Criteria:	
Subjects enrolling into Study 270 from Study 248 will have fulfilled the inclusion and exclusion criteria for Study 248.
 
A complete list and description of inclusion and exclusion criteria is provided in Section 3.4.
 
Key inclusion criteria for Study 270 include subjects with a current diagnosis of schizophrenia, (as defined by Diagnostic and Statistical Manual of Mental Disorders, Fourth Edition, Text Revision [DSM-IV-TR] criteria), who completed the open-label extension Study 248; subjects who, in the investigator's judgment, may benefit from continued participation in aripiprazole IM Depot study; and subjects who have an outpatient status. The baseline visit for Study 270 (which is the Week 52 visit of Study 248) and the first injection for Study 270 must occur within 4 weeks (which is defined as 28 [-2/+10] days) of the last injection in Study 248.
 
Key exclusion criteria include subjects with a current DSM-IV-TR diagnosis other than schizophrenia, including schizoaffective disorder, major depressive disorder, bipolar disorder, delirium, dementia, amnesic or other cognitive disorders; subjects who are known to be allergic, intolerant, or unresponsive to prior treatment with aripiprazole or other quinolinones; dependence on substances of abuse; a history of violent behavior, seizures, neuroleptic malignant syndrome, clinically significant tardive dyskinesia, or other medical condition that would expose the subject to undue risk or interfere with study assessments; involuntary incarceration; electroconvulsive therapy within 180 days prior to entry; clinically significant abnormalities in laboratory test results, vital signs, or ECG results; require hospitalization; may require any other antipsychotic medication, varenicline, cytochrome P450 (CYP) 2D6 or CYP3A4 inhibitors, or CYP3A4 inducers during the study; and if aripiprazole IM Depot (including generic formulation) is commercially available in the country where the study is being conducted.

Trial Site(s):	Approximately 250 sites globally (the number of sites globally in Study 248). New sites will not be used.
Investigational Medicinal Product(s), Dose, Dosage regimen, Treatment period, Formulation, Mode of Administration:	
The investigational products will be aripiprazole IM Depot 400 mg supplied as lyophilized vials. Both doses of aripiprazole IM Depot used in this trial (400 mg and 300 mg) will be obtained from the 400-mg lyophilized vials. IM Depot will be administered every month (study months are every 4 weeks which is defined as 28 [-2/+10] days). All doses of IM Depot must be injected into the gluteal muscle, and care must be taken to avoid inadvertent injection into a blood vessel.

Protocol 31-10-270

Trial Assessments:	
Safety: Safety will be assessed by adverse event and concomitant medication reporting at baseline (post-IM administration) and at each subsequent monthly injection visit (study months are every 4 weeks which is defined as 28 [-2/+10] days). The C-SSRS will be used to assess suicidality at baseline and at each subsequent monthly injection visit. Extrapyramidal symptoms will be assessed using the AIMS, SAS, and BARS assessment questionnaires at baseline, every 6 months, at the discretion of the investigator at any subsequent visit, and at Study Completion or the Early Termination visit. Clinical laboratory tests will be performed at baseline, every 12 months, and at Study Completion or the Early Termination visit. Vital signs will be assessed every 6 months and at Study Completion or the Early Termination visit. Body height and weight, body mass index (BMI), and waist circumference will be assessed at baseline; body height, weight, and waist circumference will be reassessed every 12 months; and body height and weight will be assessed at Study Completion or the Early Termination visit. For WOCBP, a urine pregnancy test will be administered at baseline, every 3 months, and at Study Completion or the Early Termination visit.
 
Efficacy: Efficacy will be evaluated using the CGI-S administered every 6 months.

Criteria for Evaluation:	
Safety Endpoints:
 
 • Frequency and severity of adverse events, serious adverse events (clinical and laboratory) and discontinuations from the study due to adverse events. • Suicide risk as assessed and classified by the C-SSRS. • Extrapyramidal symptoms will be evaluated by calculating the mean change from baseline in AIMS, SAS, and BARS. • The incidence of clinically significant changes will be calculated for vital signs. Mean change from baseline and incidence of clinically significant changes will be calculated for body weight and waist circumference. 
Efficacy Endpoint:
 
 • CGI-S score will be evaluated by calculating mean change from baseline.
Statistical Methods:	Due to the open-label single-arm nature of the study, all data on safety and efficacy/outcome will be summarized by descriptive statistics (eg, mean, standard deviation, maximum, minimum, and proportions).
Trial Duration:	
Subjects will continue to receive aripiprazole IM Depot in this open-label rollover study until there are clinical and/or administrative reasons for discontinuation of the subject's study treatment or until the study end date of 31 Dec 2018 is reached, whichever occurs first (see "Trial Design" section above).
 
Once aripiprazole becomes available commercially at any dosage (including generic formulation[s]) in the country where the study is being conducted, the commercial availability of aripiprazole IM Depot is terminated by the sponsor, or until the study end date of 31 Dec 2018 is reached, treatment will be discontinued. If aripiprazole IM Depot is commercially available or if the availability of aripiprazole IM Depot is terminated by the sponsor, then the subject will discontinue treatment within approximately 6 weeks of last injection for clinical transition purposes.

Protocol 31-10-270

Table of Contents

Protocol Synopsis	3
Table of Contents	7
List of In-text Tables	11
List of In-text Figures	12
List of Appendices	13
List of Abbreviations and Definitions of Terms	14
1 Introduction	16
1.1 Nonclinical Data	18
1.2 Clinical Data	20
1.3 Known and Potential Risks and Benefits	22
2 Trial Rationale and Objectives	24
2.1 Trial Rationale	24
2.2 Trial Objectives	25
3 Trial Design	25
3.1 Type/Design of Trial	25
3.2 Treatments	28
3.3 Trial Population	29
3.4 Eligibility Criteria	29
3.4.1 Informed Consent	29
3.4.2 Inclusion Criteria	30
3.4.3 Exclusion Criteria	30

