3.9 Definition of Completed Subjects

The treatment period is defined as the time period during which subjects are evaluated for primary and/or secondary objectives of the trial irrespective of whether or not the subject actually received all doses of the study medication. Subjects who are evaluated at the last scheduled visit during the treatment period will be defined as trial completers. Subjects who have their last visit by 31 Dec 2018, because they have reached the end of the study, will be defined as completers. For purposes of this trial, subjects who discontinue due to the commercial availability of study drug in the country where the study is being conducted will be defined as completers. In addition, subjects in countries where a managed access program is available for continued treatment with aripiprazole at the time of trial closure in their respective country, regardless of whether they transition to a managed access program, will also be defined as completers. Protocol-specified post-treatment follow-up contacts will not qualify as “last scheduled” visit.

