## **5.2 Disposition of Subjects**

Disposition of subjects for the enrolled sample will be summarized by region, country and center. Subject duration by month and reason for discontinuation will be tabulated for the enrolled sample. Subjects who are evaluated at last scheduled visit during the treatment period are defined as completers. Subjects who are evaluated at the last scheduled visit during the treatment period are defined as completers, i.e., subjects who have their last scheduled visit, or who discontinue due to the commercial availability of trial drug in the country are defined as completers.

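### Crude completion and discontinuation percentages mix country launch timing with drop-out, and no time-to-discontinuation display is planned to separate them

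*Protocol*

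**What the plan says.** Treatment length is set by country and calendar. The synopsis objective reads "Subjects can receive this treatment until aripiprazole IM Depot is commercially available in any dosage (including generic formulation[s]) in the country", or until 31 Dec 2018. The visit schedule (protocol Table 3.6-1, footnote b) runs to Study Month 104.

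Protocol 3.9 names three administrative routes to completion:

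- Launch: "subjects who discontinue due to the commercial availability of study drug in the country where the study is being conducted will be defined as completers".
- Calendar end: "Subjects who have their last visit by 31 Dec 2018, because they have reached the end of the study, will be defined as completers".
- Managed access: "subjects in countries where a managed access program is available for continued treatment with aripiprazole at the time of trial closure in their respective country", and this applies "regardless of whether they transition to a managed access program, will also be defined as completers".

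SAP 5.2 names the last scheduled visit and launch (subjects "who discontinue due to the commercial availability of trial drug in the country are defined as completers") but does not mention managed access. Protocol 3.7.3, item 9, lists launch among the criteria for mandatory withdrawal.

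For analysis, SAP 5.2 plans disposition by region, country and center, and adds: "Subject duration by month and reason for discontinuation will be tabulated for the enrolled sample". The outputs are CT-1.1 to CT-1.3 and CT-2. AE discontinuation, one of the three primary measures in protocol 7.3, is tabulated as incidence in CT-8.6.1 to CT-8.6.3. SAP 5.1.1 limits categorical variables to frequency and percentage. Neither SAP section 5 nor the Appendix 4 table list contains a time-to-event estimate, a censoring rule or numbers at risk for discontinuation.

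**The concern.** A subject in a country with an early launch has only a short time in which to drop out before being counted as a completer. A subject in a country that never launches may have to stay for years. Two countries whose subjects leave at the same rate can therefore show very different completion percentages, and the pooled figure depends on the mix of launch dates.

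AE discontinuation has the same weakness: a crude incidence rises with the time available to observe it, and that time is set by country. A reader of the study report who wants to know how long subjects stay on depot, or how often they stop for AEs by a given time, could not get this from the planned summary tables.

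**Working it through.** **Inputs from the documents.** Completer rules: protocol 3.9 and SAP 5.2. Longest scheduled follow-up: 104 study months × 28 days = 2912 days, and 2912 / 365.25 = 8.0 years. Anticipated enrolment: 500 to 800.

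**Inputs not in the documents.** No drop-out rate, launch date, country mix or expected completion rate is given, so there is no plan figure to reproduce. What follows illustrates a mechanism under assumed values.

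**Step 1. Same drop-out, different launch.** Let h be a constant non-administrative drop-out per study month and T the month of administrative exit. The completer share is C = (1 − h)^T.

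| h per study month | T = 6 | T = 60 | T = 104 |
|---|---|---|---|
| 0.5% | 97.0% | 74.0% | 59.4% |
| 1% | 94.1% | 54.7% | 35.2% |
| 2% | 88.6% | 29.8% | 12.2% |

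**Step 2. Pooled figure.** Take h = 1% and launches at Months 6 and 60. With 25% of subjects in the early-launch group, completion is 0.25 × 94.1 + 0.75 × 54.7, about 65%. With 75% it is 0.75 × 94.1 + 0.25 × 54.7, about 84%. Drop-out is unchanged.

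**Step 3. The percentage still carries drop-out information.** Reading down the T = 60 column, completion falls from 74.0% to 29.8% as h rises. The two influences are confounded, and neither is absent. Different persistence can even give one answer: 10% per year with launch at 36 calendar months gives 0.9^3 = 72.9%, and 20% per year with launch at 17 months gives 0.8^(17/12) = 72.9%.

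**Step 4. AE discontinuation.** If a fixed fraction q of drop-outs is for AEs, the crude incidence is q × (1 − C). At h = 1% this is q × 5.9% for launch at Month 6 and q × 45.3% at Month 60. The ratio is 45.3 / 5.9 = 7.7 whatever q is, with the same AE discontinuation rate per month.

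**Step 5. Would a monthly count help?** Assume 20% drop-out per year, half the subjects with launch at 12 months and half at 36. At 24 months, 0.5 × 0.8^2 = 32% are still on study. The share who would still be on depot without launch is 0.8^2 = 64%. In a simulation (650 subjects, the midpoint of 500 to 800; 200 runs), Kaplan-Meier with launch exits censored gave 63.9% on average. Crude completion in this mix is (80.0 + 51.2) / 2 = 65.6%, a figure tied to no fixed time. The simulation assumes one drop-out rate in every country.

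**The case against.** The best defence is that this is a single-arm access rollover whose primary objective is to keep supplying the drug. Protocol 7.3 and 7.4 name neither completion nor retention as a measure. Against the supply objective, a subject treated until local launch is a success, so counting that subject as a completer is deliberate. The percentage misleads only if it is read as persistence, and neither document proposes that reading. This stands, and it limits the weight of the point. It does not cover AE discontinuation, which is a primary measure with the same unequal follow-up.

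Second, the plan holds more than percentages of completers. CT-1.2 splits disposition by country, CT-2 gives reasons, CT-7.1 to CT-7.3 describe exposure by injection, and by-subject listings (DREAS-1, PDATA-3, PDATA-7) are planned. A reader might infer that nothing on duration is planned, and that would be wrong. But none of these outputs has a stated censoring rule, and splitting by country does not make countries with different launch dates comparable. A reader might also infer that CT-1.3 merges launch exits with clinical exits. Only its title and one sentence in SAP 5.2 are available, so its layout is unknown.

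Third, the numbers are hypothetical, and Month 104 is the end of the visit schedule, not a known launch date. This is true, and it is why a range is shown.

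Fourth, Kaplan-Meier is not a complete cure. Once early-launch countries are censored, the late part of the pooled curve rests on late-launch countries. If drop-out differs between countries, pooled late retention again depends on the launch mix. The CRF reason categories are not shown either, and protocol 3.7.3, item 4, groups requests by subject, investigator, sponsor and regulator. Both points stand and belong in the fix.

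**Conclusion.** The concern holds: the planned crude disposition and discontinuation percentages, including those for AE discontinuation, mix launch timing with drop-out and cannot be read as persistence on depot. Under constant drop-out of 1% per study month, assumed equal in all countries, completion ranges from 94% to 35% across exits at Months 6 to 104. Over 0.5% to 2% the same exits give 97% to 59% and 89% to 12%. The direction follows from the completer rule; the size depends on launch dates and drop-out rates that the documents do not give.

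Two stronger readings are tempting and unsupported. One is that the completion rate shows launch timing and says nothing about how long subjects stay; step 3 shows that it depends on both. The other is that the plan fails to measure its primary objective; that objective is continued supply, and retention is not a stated endpoint. No stated figure is wrong. This is a worthwhile, inexpensive improvement.

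**What to change.** In SAP 5.2:

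1. Add a descriptive Kaplan-Meier estimate of time from the first Study 270 injection to non-administrative discontinuation. Censor at launch, country closure (with or without managed access), sponsor termination and 31 Dec 2018. Protocol 3.1 already separates clinical from administrative reasons. State how each CRF reason maps to event or censoring, including the mixed category in protocol 3.7.3, item 4.
2. Report estimates at fixed times with numbers at risk, overall and by region. Give the times in days: twelve protocol months are 12 × 28 = 336 days, which falls outside the SAP window for Month 12 (days 348 to 379).
3. Add cumulative incidence of AE discontinuation and of the other reasons, treating the remaining clinical reasons as competing events.
4. Show administrative exits on their own line in CT-1.1 and CT-1.2.
5. Reconcile the completer definition across protocol 3.9 (includes managed access), SAP 5.2 (omits it) and protocol 3.7.3, item 9 (launch as a withdrawal criterion), so that each exit has one disposition category.

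The cost is SAP wording and one or two extra outputs. Injection dates are recorded on the CRF (protocol 3.11) and discontinuation reasons are already to be listed. The display is descriptive, so it fits a plan with no formal testing. Two caveats should be printed with it: censoring at launch assumes that launch timing is unrelated to drop-out, and late pooled estimates rest on late-launch countries.
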